Based on participant responses to the questions, research personnel will determine preliminary eligibility for an on-site visit. If it appears the participant meets the preliminary eligibility, an on-site visit will be scheduled, and a consent form will be mailed / emailed to the participant for their consideration and review. After the study participant has had several days to review the consent form, research personnel will call the participant to answer any further questions regarding the consent form. Participants will be enrolled in small ( $n = 9$ ) cohorts or "waves" to facilitate social support and adherence to the supervised exercise training sessions. We anticipate having 9 waves to successfully reach our target  $n$ . This assumes that each wave will have 4 participants, hence, 4 participants x 9 waves = 36 total participants.

At the on-site screening visit, research personnel will once again cover inclusion/exclusion criteria, study procedures, requirements, and risks. Following written informed consent, participants will have their body weight and standing height measured to determine their body mass index (i.e., 25.0-39.9 kg/m^2). Current prescription drug use will be recorded by having

participants physically bring their prescription labels or medication bottles to the testing site. Additionally, participants will complete a Medical History Questionnaire (see attachments).

Written authorization will be obtained from consented participants to allow research personnel to contact the participant's primary care physician to receive physician's clearance prior to study testing visits. The physician will be asked to provide their assent or dissent for their patient to participate in the exercise testing protocols and supervised group exercise sessions involved with this study. They will have the option to indicate any modifications that may be necessary for the patient to participate safely. The Physician Clearance Form (see attachments) will be faxed to the patient's physician following the screening visit.

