Participants will perform baseline assessments (**Visits 1-2**) prior to randomization. Subsequently, participants will be randomly selected to: 1) control (EX only) or 2) BR+EX. Group allocation will be determined at random using a computer-based number generator in blocks of 2 to ensure equal between-group distribution (i.e.  $n = 2$  Ex only;  $n = 2$  BR+EX). Each number will be kept in a sealed envelope until completion of **Visits 1-2**.

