**6-Minute Walk Test-** Consistent with standard procedures (20), participants will be instructed to walk for six minutes around an indoor, closed course during **Visits 2 and 3**. A chest-strap heart rate monitor will be worn to measure changes in heart rate before and after walking, and a triaxial accelerometer will be used to examine signal profile associated with movement complexity (i.e. movement accelerations) and estimates of energy expenditure (kilocalories). The accelerometer will be worn on the non-dominant hip and fastened with an elastic belt. Subjects will additionally be asked to identify their level of perceived exertion on a continuous visual analog scale (“no exertion” to “maximal exertion”) after the test.

**Supervised Exercise Training (CrossFit, Bloomington)-** Participants randomized to exercise training will perform combined aerobic and resistance workouts in a group setting with a cohort of approximately 4 women also enrolled in the study. There is a chance that participants will complete the exercise training sessions with other individuals who are not enrolled in the study. This will be outlined in the Informed Consent Statement provided to participants.

Full participation in the exercise training intervention is defined as attending 3 sessions per week for a total of 8 weeks (24 sessions total). The sessions will be supervised by a certified fitness professional who will make adjustments to the workouts based on individual needs/abilities. Each one-hour session will consist of a warm-up, instruction of the workout, a workout of combined aerobic and resistance training exercises, and cool-down. Intensity of the exercise sessions will be progressed gradually from weeks 1 to 8 and monitored by having participants identify their rating of perceived difficulty for each session using a discrete visual analog scale (0-10). The intensity of exercise sessions will also be monitored through continuous heart rate assessment (Actiheart) during week 2, week 4, and week 6 of training.

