### **12.0 Statistical Considerations**

Rather than confirm efficacy, this proposal addresses elements of feasibility such that we intend to generate preliminary effect sizes for a larger-scale investigation. Descriptive statistics and calculation of rates (e.g., recruitment, retention, adherence, and adverse event) will be used for study aim 1. Between-group differences in descriptive data along with aims 2(a,b) and 3 will be evaluated using an unpaired t-test. Effect size calculations will be performed with Cohen's  $d$  to qualify substantive differences: small (0.2), medium (0.5), and large (0.8). Potential covariates of interest include age, body mass, body fat percentage, and/or markers of inflammation. Non-normally distributed data will be log-transformed. Two-tailed parametric correlations (Pearson) will be performed and based on consequent results, multiple linear regression will be used to examine changes in inflammation, endothelial function, distance in 6-minute walk test, leg strength, and resting blood pressure/arterial stiffness.

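### Section 12.0 compares arms with an unpaired t-test that ignores training wave and baseline; if outcomes correlate positively within waves, the test is conservative and loses some precision

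*Combined protocol and SAP*

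**What the plan says.** Section 12.0 plans one between-arm test for the secondary and tertiary aims: differences in descriptive data, "along with aims 2(a,b) and 3 will be evaluated using an unpaired t-test". It does not say whether the tested value is the change or the post-intervention value. On adjustment it says: "Potential covariates of interest include age, body mass, body fat percentage, and/or markers of inflammation". Wave, block and the baseline value of the outcome are not on that list. The regression mentioned afterwards depends on correlation results and does not name them either.

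Section 6.0 describes how women enter. They come in waves, formed "to facilitate social support and adherence to the supervised exercise training sessions". On numbers it says "We anticipate having 9 waves to successfully reach our target" and then "This assumes that each wave will have 4 participants, hence, 4 participants x 9 waves = 36 total participants". The same paragraph also gives a cohort size of 9. Allocation uses a "computer-based number generator in blocks of 2 to ensure equal between-group distribution", with 2 EX and 2 BR+EX as the example, which is one wave of 4.

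Section 7.0 (Supervised Exercise Training) has women exercise "in a group setting with a cohort of approximately 4 women also enrolled in the study". It adds that people outside the study may be present.

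Sections 3.2 and 3.3 define success for Aims 2 and 3 by statistical significance. Section 12.0 says the purpose is preliminary effect sizes, not confirmation of efficacy. Section 3.1 sets project success at 20 of 24 randomized women completing training.

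**The concern.** If each wave holds equal numbers from both arms, anything the women in a wave share (calendar period, group dynamics, the mix of sessions) affects both arms equally and drops out of the arm difference. The unpaired t-test treats all women as one unstructured sample, so it still counts that shared variation as error. When the within-wave correlation is positive, the reported standard error is then larger than the real sampling variability of the difference. The test rejects less often than its nominal level, and precision that the design has already secured is not used.

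The stakes are moderate. The trial is small and its success statements depend on p-values. Any confidence intervals passed on to the larger study would be wider than necessary.

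**Working it through.** **Inputs from the documents.** 9 waves, 4 women per wave, 36 in total (Section 6.0); 2 women per arm per wave (Section 6.0, example); 20 of 24 completing (Section 3.1). The plan's own figures reproduce: 4 × 9 = 36 and 20/24 = 83.3%. Dropout at that threshold is 4/24 = 16.7%, or 6 of 36.

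**Assumed input.** The within-wave correlation ρ of the analysed outcome. The documents give none, so a range is shown. No alpha is stated; a two-sided 5% level is assumed.

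**Formulas.** Set the total variance to 1, with n women per arm, 2 per wave.
- True variance of the arm difference: 2(1 − ρ)/n, because the wave effect cancels.
- Average variance that the t-test estimates: (2/n)[1 − ρ/(n − 1)]. Each woman shares her wave with one other woman in her arm, so the within-arm sample variance averages 1 − ρ/(n − 1).
- Ratio of t-test SE to true SE: √{[1 − ρ/(n − 1)]/(1 − ρ)}.

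**Example, n = 18, ρ = 0.2.** True SE = √(2 × 0.8/18) = 0.298. T-test SE = √[(2/18)(1 − 0.2/17)] = 0.331. Ratio = 1.111.

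**Results, 36 women in 9 complete waves.** Type I error and power come from 40,000 simulated trials per setting. The comparison model has wave as a fixed effect and no baseline term.

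| ρ | True SE | t-test SE | Ratio | t-test type I error | Power at d = 0.5, t-test / wave model | CI width, t-test ÷ wave model |
|---|---|---|---|---|---|---|
| 0 | 0.333 | 0.333 | 1.000 | 4.8% | 31% / 31% | 0.989 |
| 0.05 | 0.325 | 0.333 | 1.024 | 4.5% | 30% / 31% | 1.013 |
| 0.10 | 0.316 | 0.332 | 1.051 | 4.0% | 30% / 33% | 1.039 |
| 0.20 | 0.298 | 0.331 | 1.111 | 3.1% | 29% / 36% | 1.099 |
| 0.30 | 0.279 | 0.330 | 1.185 | 2.4% | 29% / 41% | 1.171 |

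The wave model's type I error stayed near 5% throughout (4.8% to 5.1%). With 24 women in 6 complete waves the SE ratios for ρ = 0.05 to 0.30 are 1.024, 1.049, 1.108 and 1.179.

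**Cost of a fixed wave term, complete waves, ρ = 0.** Residual degrees of freedom fall from 34 to 26 and the critical value rises from 2.032 to 2.056, so the interval widens by about 1%. With 24 women it rises from 2.074 to 2.110, about 2%.

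**Cost with dropout.** Random dropout at the rate in Section 3.1 breaks the 2 + 2 balance. Interval width, fixed wave model ÷ t-test (4,000 simulated trials per setting):

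| ρ | 30 of 36 women, 9 waves | 20 of 24 women, 6 waves |
|---|---|---|
| 0 | 1.047 | 1.056 |
| 0.05 | 1.022 | 1.031 |
| 0.10 | 1.000 | 1.009 |
| 0.20 | 0.942 | 0.950 |

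The fixed term therefore costs about 5% at zero correlation and breaks even near ρ = 0.10.

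**Effect on Cohen's d.** The pooled SD changes by the factor √[1 − ρ/(n − 1)]. At ρ = 0.2 and n = 18 this is √(1 − 0.2/17) = 0.994, a shift of 0.6%. The mean difference is unbiased.

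**The case against.** The strongest objection is that the correlation is wholly assumed. That stands. At ρ = 0 the t-test is correct, and a negative correlation reverses the sign: at ρ = −0.05 the ratio is √[(1 + 0.05/17)/1.05] = 0.977, so the t-test SE would be about 2% too small. A reader might infer that the standard errors simply are too large; the documents support that only conditionally. Shared sessions and intended social support make a positive value plausible. A shared trainer per wave does not help the argument, because Section 7.0 mentions only a certified fitness professional and never ties one to a wave.

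Second, balance within waves is inferred. Section 6.0 does not say that allocation is stratified by wave, and a cohort of 9, also given there, cannot split evenly. This stands as a limit on exactness.

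Third, a reader might infer that adjusting for wave costs only about 1%. That holds for complete waves. With the dropout that Section 3.1 tolerates, a fixed term costs about 5% when wave has no effect.

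Fourth, a reader might infer that the effect sizes themselves are distorted, or that group training inflates false positives. Neither follows. The planned product is Cohen's d, which hardly changes, and Section 12.0 schedules no confidence intervals. Because both arms sit in each wave, positive correlation makes the test conservative.

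What survives is that p-values are planned and used to declare success, and that the analysis omits the grouping within which allocation appears to be balanced.

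**Conclusion.** The point holds in conditional form. Given positive within-wave correlation and waves balanced 2 + 2, the planned t-test is conservative. Its standard error is about 2% to 11% too large for assumed correlations of 0.05 to 0.2, and about 18% too large at 0.3. The damage is confined to p-values and any intervals reported.

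The figures describe wave adjustment alone. With baseline in the model, the relevant correlation is the residual one after baseline is accounted for, which may be smaller. The gain would also shrink if the beetroot effect itself differed between waves. This is a worthwhile, inexpensive refinement and not a threat to the trial's validity.

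**What to change.** In Section 12.0, replace the unpaired t-test for Aims 2a, 2b and 3 with a linear model of the post-intervention value on arm and the baseline value of the outcome, with wave as a random intercept. Report the arm difference with its confidence interval. Cohen's d can still be reported, with its denominator stated as the total SD.

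A random intercept is preferred to fixed wave terms because it can recover information from waves left incomplete by dropout. That preference rests on reasoning; its cost was not calculated. With 6 to 9 waves the wave variance may be estimated as zero, so the plan should say in advance that the model then reduces to arm plus baseline, and should name a small-sample method for the degrees of freedom.

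The cost is a sentence or two in Section 12.0, a model that SPSS (named in Section 10.0) can fit, and no new data beyond a recorded wave identifier for each woman.

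Section 6.0 should also state whether allocation is balanced within each wave and reconcile the wave size (9 or 4). The randomized total should be reconciled between Section 3.1 (24) and Section 6.0 (36).

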## **2.0 Objective(s)**

### **2.1 Primary Objective**

**Aim 1.** Determine the feasibility of an 8-week (3x/week) exercise training progression (EX) coupled with the consumption of beetroot juice (BR+EX) prior to exercise in postmenopausal women. Prior work supports daily, short-term (21 days) consumption of beetroot juice in men and women aged 62 +/- 1 years, yet this was performed in the absence of exercise training. Research unequivocally supports the utility of exercise training, still in the context of this proposal, feasibility is unknown.

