### **2.2 Secondary Objective**

**Aim 2a.** Determine preliminary effects sizes for pre-exercise beetroot juice consumption + exercise training (BR+EX) compared + exercise training only (EX) on distance (feet) covered during a 6-minute walk test. Performance during the 6-minute walk has been shown to accurately estimate peak oxygen uptake (i.e., aerobic fitness) and functional mobility. Consistent with others showing performance benefits of pre-exercise beetroot juice consumption and acute exercise, we anticipate a small to medium effects size in a beneficial direction (i.e., greater positive change) for BR+EX compared to EX.

**Aim 2b.** Determine preliminary effect sizes for BR+EX compared to EX on improvement of endothelial-dependent vasodilation as evidenced by percent increase in flow-mediated dilation. Based on our working premise that beetroot juice may offset the burdens of endothelial dysfunction/activation by increasing nitric oxide bioavailability, coupled with the effects of exercise training, we anticipate a small to medium effect size in a beneficial direction for BR+EX compared to EX.

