### **3.0 Outcome Measures/Endpoints**

#### **3.1 Primary Outcome Measures**

Outcomes of interest include recruitment, retention, adherence (i.e., exercise prescription and assessments), perceived exercise difficulty, and adverse event rates. Project success will be based on 83% [20 of 24] of randomized participants completing 8 weeks of exercise training.

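### Aim 2 and 3 effect sizes are planned as Cohen's d point values with small/medium/large labels and no interval, though at 10 to 18 women per arm the sampling error exceeds the spacing of the labels

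*Combined protocol and SAP*

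**What the plan says.** Section 12.0 sets efficacy aside and states "we intend to generate preliminary effect sizes for a larger-scale investigation". For Aims 2a, 2b and 3, group differences "will be evaluated using an unpaired t-test". Then "Effect size calculations will be performed with Cohen's" *d*, used "to qualify substantive differences: small (0.2), medium (0.5), and large (0.8"). No confidence interval, standard error or small-sample correction for d is named in any section.

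Section 2.2 gives the expected size for Aim 2a: "we anticipate a small to medium effects size in a beneficial direction". Sections 2.2 and 2.3 repeat that expectation for Aims 2b and 3. The primary objective in Section 2.1 is feasibility, so the effect sizes are a stated purpose beside the primary aim.

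Two sample sizes appear. Section 3.1 has "Project success will be based on 83% [20 of 24] of randomized participants completing 8 weeks of exercise training"; Section 6.0 has "4 participants x 9 waves = 36 total participants". Allocation is equal (Section 6.0). There is no power or precision calculation.

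**The concern.** The effect sizes are meant for use in planning another study, and the only rule for interpreting them is to place a point value on a three-mark scale. The marks are 0.3 apart. If the standard error of d is larger than that, the label says little about the true effect. A medium, large or negative result could easily arise by chance from the same underlying effect, and nothing in the planned report would show this. At stake is what Aims 2 and 3 can conclude, and what the planners of a larger study would take from them.

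**Working it through.** **Inputs from the documents.** 24 randomized and 20 completing (Section 3.1); 36 in all (Section 6.0); equal allocation (Section 6.0); marks at 0.2, 0.5 and 0.8 (Section 12.0); expected effect small to medium (Sections 2.2 and 2.3), so about 0.2 to 0.5.

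**Stated figures.** 20/24 = 83.3% and 4 × 9 = 36; both reproduce. Equal arms give 20/2 = 10, 24/2 = 12 and 36/2 = 18 per arm.

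**Assumptions.** Normal data with a common SD; d formed from the between-group difference in change; two-sided 95% intervals; 0.2, 0.5 and 0.8 read as lower cut-points. The plan states none of these. The true effect is set at 0.35, the middle of the expected range.

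**Standard error.** SE(d) = √(2/n + d²/(4n)), with n per arm and d = 0.35:
- n = 10: √(0.2000 + 0.0031) = 0.45
- n = 12: √(0.1667 + 0.0026) = 0.41
- n = 18: √(0.1111 + 0.0017) = 0.34

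All exceed the 0.3 between marks.

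**Intervals and label probabilities.** The statistic d√(n/2) follows a noncentral t distribution with 2n − 2 degrees of freedom and noncentrality δ√(n/2), where δ is the true effect. Inverting it gives exact intervals; evaluating it at δ = 0.35 gives the probabilities.

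| | 10 per arm | 12 per arm | 18 per arm |
|---|---|---|---|
| 95% CI, observed d = 0.50 | -0.40 to 1.38 | -0.32 to 1.31 | -0.17 to 1.16 |
| True 0.35: estimate in 0.2–0.5 | 26% | 28% | 34% |
| True 0.35: estimate 0.8 or more | 17% | 15% | 10% |
| True 0.35: estimate negative | 22% | 20% | 15% |

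**Sensitivity to the band edges.** Suppose each estimate takes the label of its nearest mark instead (edges 0.1, 0.35 and 0.65). A true 0.2 is then mislabelled in 78% of trials at 10 per arm and 71% at 18; a true 0.5 in 75% and 66%. The conclusion does not depend on the choice of edges.

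**What this means for planning.** Assume 80% power and two-sided 5%, so n per arm = 2(1.960 + 0.842)²/d² = 15.70/d².
- d = 0.50: 15.70/0.25 = 62.8, so 63 per arm.
- d = 1.38, the upper limit at 10 per arm: 8.2, so 9 per arm.
- d = 1.16, the upper limit at 18 per arm: 11.7, so 12 per arm.
- The lower limits are negative and give no sample size.

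The label medium alone hides this range.

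**Small-sample correction.** Hedges' factor is J = 1 − 3/(4·df − 1):
- df = 18: 1 − 3/71 = 0.958
- df = 22: 1 − 3/87 = 0.966
- df = 34: 1 − 3/135 = 0.978

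So g is about 4%, 3% and 2% below d. Using g moves the 0.2–0.5 rate only from 28.1% to 29.0% at 12 per arm and from 34.2% to 34.9% at 18. The rate of negative estimates does not change, because g only rescales d.

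**The case against.** The primary aim is feasibility, with its own success criterion in Section 3.1. The effect sizes are called preliminary, and Section 12.0 disclaims confirming efficacy. The planned t-test also guards partly against reading a chance estimate as real. Means, SDs and counts, if reported, would let any reader compute the interval later. The design of the larger study belongs to its own protocol. All of this stands, and it keeps the point minor. It does not justify the label: a p-value gives no range of plausible effects, and the plan should not leave the interval to its readers.

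Four stronger readings might be inferred, and the documents support none of them.
- *The missing correction or interval makes the label wrong.* It does not. Sampling error at this size does. An interval shows that error without reducing it, and g leaves mislabelling almost unchanged.
- *The next trial would be too small on average.* This would follow from squaring J (0.932 at 12 per arm, 0.956 at 18) as if d were a fixed multiple of the truth. But uncorrected d exceeds a true 0.35 in only 50.4% and 50.3% of trials, and sample size varies as 1/d², so upward bias in d does not establish an average shortfall.
- *Cohen's d is the trial's main product.* Section 2.1 makes feasibility primary.
- *The larger study will be sized from the point value or label.* No section says so. The plan simply offers nothing else in its place.

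**Conclusion.** The point holds as a minor but real weakness in the analysis of Aims 2a, 2b and 3. At every size the documents imply, the standard error of d (about 0.34 to 0.45) exceeds the 0.3 between labels, and the interval around a medium result runs from below zero to above 1.1. With a true effect in the middle of the expected range, the estimate falls outside 0.2–0.5 in about two-thirds to three-quarters of trials (66% at 18 per arm, 74% at 10).

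This rests on equal arms, normal data with a common SD, and the assumed band edges. It does not depend on whether 24 or 36 is the intended number, though Sections 3.1 and 6.0 should be reconciled. The feasibility aim is unaffected.

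**What to change.** In Section 12.0, replace the labelling rule with a sentence to this effect: each Aim 2 and Aim 3 effect size will be reported with its 95% confidence interval, the small/medium/large labels will not be used as conclusions, and the interval is what will be carried forward to planning the larger study. The sentence should also say what d is computed on (for example, the difference in change scores).

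Hedges' g may be used in place of d if wished; it lowers the reported value by about 2 to 4% and does not reduce mislabelling.

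The cost is one sentence, with no new data, visits or participants. The reported effects will look less certain, which is an accurate picture at this size.

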#### **3.2 Secondary Outcome Measures**

**2a.** The distance (feet) covered during a 6-minute walk test at baseline prior to the intervention and following BR+EX is the main secondary outcome of interest. To confirm the relationship of the functional 6-minute walk test to aerobic fitness, measures of oxygen consumption (ml/kg/min or L/min), heart rate (bpm), and blood pressure (mm Hg) will be taken during constant speed walking at a typical walking pace prior to the 6-minute walk test. Additionally, functional mobility will be assessed by analyzing triaxial movement patterns from an accelerometer worn on the non-dominant hip during the 6-minute walk test.

The BR+EX intervention will be considered successful in the event that there is a statistically significant increase in 6-minute walk distance (feet) along with a decrease in oxygen consumption (ml/kg/min or L/min), decrease in exercising heart rate (bpm), improvement in heart rate recovery following exercise (post exercise heart rate – heart rate 1 min, 2 min after exercise (bpm)), decrease in exercising blood pressure (mm Hg), decrease in post-exercise blood pressure (mm Hg), and/or improvement in gait function (i.e. preferred walking speed, center of mass characteristics) from baseline to post-intervention above any improvement seen in EX.

**2b.** Percent changes in brachial artery diameter (%), cutaneous vascular conductance (%), and pulse wave velocity (m/s) at baseline prior to the intervention and following BR+EX are secondary outcomes of interest, representing changes in endothelial dependent vasodilation. A non-invasive technique of flow mediated dilation of the brachial artery using ultrasound imaging will be used to assess the percent change in vessel diameter following occlusion. A local heating protocol using non-invasive Laser Doppler flowmetry in conjunction with blood pressure measurements will be used to obtain measures of red blood cell (RBC) flux and mean arterial pressure (MAP) to calculate cutaneous vascular conductance (RBC flux/ MAP). The velocity of the pulse wave traveling from the carotid to femoral artery will be assessed non-invasively using tonometry.

A statistically significant increase in the percent change in brachial artery diameter (%), cutaneous vascular conductance (%), and/or a decrease in pulse wave velocity (m/s) in BR+EX above any improvement observed in EX from baseline to post-intervention will be considered a successful outcome.

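### The rule to log-transform non-normal data names no scale and no fallback, yet several outcomes it covers can be zero or negative

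*Combined protocol and SAP*

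**What the plan says.** Section 12.0 gives one unqualified sentence on distributional problems: "Non-normally distributed data will be log-transformed". It lists no variables, test of normality, offset or alternative method.

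The same section specifies the comparison: "Between-group differences in descriptive data along with aims 2(a,b) and 3 will be evaluated using an unpaired t-test". That sentence does not name the quantity compared. Other text points to change from baseline:

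- Section 2.2, Aim 2a: "we anticipate a small to medium effects size in a beneficial direction (i.e., greater positive change) for BR+EX compared to EX".
- Section 3.2 judges the walk-test outcomes "from baseline to post-intervention above any improvement seen in EX", and for arterial stiffness looks for "a decrease in pulse wave velocity (m/s) in BR+EX above any improvement observed in EX".
- Section 3.3 counts a larger fall in the plasma markers in BR+EX than in EX as success.
- Section 12.0, immediately around the log rule: "multiple linear regression will be used to examine changes in inflammation, endothelial function, distance in 6-minute walk test".

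Section 12.0 also says that the study is meant to supply preliminary effect sizes for a larger trial rather than to confirm efficacy, with Cohen's d as the measure.

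**The concern.** A logarithm does not exist at or below zero, and a change from baseline can take either sign. If the rule is applied to changes, software will typically return missing values, and whether a woman stays in the analysis then depends on her own outcome. Because the arms are expected to differ in that outcome, the loss differs by arm. In a trial of 24 women (Section 3.1) or 36 (Section 6.0), a few such losses per arm alter the effect size handed to the next trial. Even if nobody is lost, leaving the scale open allows it to be chosen after the data are seen, and that choice affects the reported d.

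**Working it through.** The documents contain no variance or power figure on this point, so there is nothing to reproduce. The shares and effect sizes below rest on assumed distributions and are illustrative.

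**Inputs.** From the documents: 24 randomised with 20 completers (Section 3.1), or 36 in total (Section 6.0), allocated equally, giving 12, 10 or 18 per arm; an anticipated small to medium effect, d 0.2 to 0.5 (Sections 2.2 and 12.0). Assumed: the mean change in EX in units of the SD of change, the shape of the changes, and the normality test.

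**Step 1. Where a log exists.**

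| Outcome | Raw value positive? | Improvement | Women lost if post minus baseline is logged |
|---|---|---|---|
| 6-minute walk distance | yes | increase | those who did not improve |
| Brachial diameter % | not necessarily; a percent change within one visit | increase | those who did not improve |
| Pulse wave velocity | yes | decrease | those who improved |
| Plasma markers | yes, if detected | decrease | those who improved |

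Brachial diameter % may have no log even at a single visit, so logging raw values first does not rescue every outcome.

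**Step 2. Share undefined if normal changes are logged.** P(change ≤ 0) = Φ(−mean/SD).

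| EX mean change (SD) | EX lost | BR+EX lost, d = 0.2 | BR+EX lost, d = 0.5 |
|---|---|---|---|
| 0 | 50% | 42% | 31% |
| 0.25 | 40% | 33% | 23% |
| 0.5 | 31% | 24% | 16% |
| 1.0 | 16% | 12% | 7% |

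Example with 12 per arm, EX mean 0.5 and d = 0.5: EX keeps 12 × (1 − 0.309) = 8.3 women and BR+EX keeps 12 × (1 − 0.159) = 10.1. For lower-is-better outcomes the shares mirror: 50% to 84% of EX and 58% to 93% of BR+EX, all improvers.

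**Step 3. How often the rule fires, and what it does then.** The rule applies only to non-normal data, so the trigger must be modelled. Assume Shapiro-Wilk at 5% in either arm, 18 per arm, mean changes of 0.5 SD (EX) and 0.85 SD (BR+EX). The true d is 0.35, midway between 0.2 and 0.5.

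- *Normal changes.* The log is triggered in about 10% of trials. Mean d goes from about 0.35 to 0.34.
- *Right-skewed changes.* Take a shifted lognormal with log-scale SD 0.8. Before rescaling to SD 1, its mean is exp(0.32) = 1.377 and its SD is √[(e^0.64 − 1)e^0.64] = 1.304. For a mean change of k SDs, P(change ≤ 0) = Φ[ln(1.377 − 1.304k)/0.8].
  - EX, k = 0.5: Φ[ln(0.725)/0.8] = Φ(−0.40) = 34%.
  - BR+EX, k = 0.85: Φ[ln(0.269)/0.8] = Φ(−1.64) = 5%.
  - In simulation the log was triggered in about 95% of trials, and mean d fell from about 0.42 to 0.15. A repeat of 8,000 trials at these settings gave 0.41 to 0.14.
- *Same skewed shape, other means.* With an EX mean of 0.25 SD, the repeat gave d of about 0.01. With an EX mean of 1.0 SD almost no value is undefined, yet d rises to 0.66, because it is now measured on a different scale.

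**Step 4. Logging raw values first.** For an illustrative positive, skewed, lower-is-better marker, log(post/baseline) existed for 100% of women. The log of the change existed for 31%, and those were the women who worsened.

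**The case against.** The strongest reply is that the sentence speaks of data, not change scores. Logging positive raw values and then differencing complies with it and loses no woman who has both measurements. The t-test sentence does not name the compared quantity, and an analyst who met undefined logs would notice them. All of this stands. A reader might infer that the plan, followed literally, drops the women who did not improve. The documents do not support that: nothing in them says that undefined logs are excluded, and for pulse wave velocity and the markers the affected women would be the improvers.

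A reader might also take a fall in d from about 0.35 to 0.22, and in power from 17% to 9%, as the cost of the rule. Those figures arise when normal changes are logged in every trial. The rule would seldom touch such data; with the Shapiro-Wilk trigger, power moves only from 17.4% to 16.9%. They should not be presented as its effect.

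It can further be said that the primary outcomes are feasibility rates, which the rule does not affect, and that baseline-adjusted models go beyond a clarification. The first is correct and limits the weight of the point, but effect sizes are a stated product of the study. On the second, naming the scale and the fallback is the essential part; the adjustment uses baseline values already collected.

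What the reply does not answer is that some outcomes can be non-positive on either reading, and the plan offers nothing for them.

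**Conclusion.** The point holds as a gap in the rule: no stated scale, no criterion for non-normality and no fallback, although the contrasts are changes and one outcome is a percent change by construction. If changes are logged, exclusion by sign follows, unequally between arms, and Cohen's d is distorted. The distortion is negligible for near-normal changes and can be large for skewed ones. Its size, and even whether d is lowered or raised, depends on distributions the documents do not give. The point concerns secondary and exploratory aims. It should be corrected before analysis, but does not threaten the primary feasibility outcome.

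**What to change.** Replace the sentence in Section 12.0 with a rule by outcome:

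1. Log-transform only strictly positive raw measurements, such as the plasma analytes, at both visits. Compare arms on the log post-value with log baseline as covariate, and report the ratio of geometric means with its confidence interval.
2. Leave changes and percent changes, including brachial diameter %, untransformed. Where they are non-normal, use a rank-based or permutation test as the check.

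State how non-normality will be judged, and name in advance which outcomes fall under each rule, so that the scale on which each effect size is reported is fixed before the data are seen. The cost is a few sentences in Section 12.0. No new data, visits or participants are needed.
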